## 1.0 PROTOCOL SUMMARY AND/OR SCHEMA

### Study Objective

- The primary objective of the study is to determine if panitumumab with hepatic arterial infusion (HAI) in combination with systemic chemotherapy can increase the recurrence free survival (RFS) for colorectal cancer patients with resected liver metastases.

### Study Population

- Eligible patients (metastatic colorectal cancer with no extra-hepatic disease immediately prior to protocol enrollment) who have liver resection and are all-RAS wild type.

### Number of Patients

- 78

### Study Design

- Randomized phase II trial

### Therapeutic Intervention

- All patients receive HAI FUDR (0.12 mg/kg/day X kg X pump volume) / pump flow rate and Dexamethasone flat dose of 25 mg on days 1.
- All patients receive CPT-11 (150 mg/m^2 IV over 30 min to an hour), Leucovorin (400 mg/m^2 IV over 30 min to an hour) and 5FU (1000 mg/m^2/day continuous infusion over two days) on days 15 and 29
- Randomization to panitumumab 6 mg/kg day 15 and 29 (or no panitumumab)
- Each cycle repeats every 36 days for a total of 6 cycles.

This phase II study aims to assess the efficacy of panitumumab with HAI in combination with systemic chemotherapy in patients with completely resected hepatic metastases from colorectal cancer. The protocol includes biological correlative studies. The primary objective of this study is to determine if the RFS increases with the addition of concurrent intravenous Panitumumab to HAI plus systemic chemotherapy after hepatic resection. This study will 1:1 randomize 78 patients who are all-RAS wild type after liver resection to HAI FUDR and dexamethasone with systemic chemotherapy, +/- systemic Panitumumab. The primary endpoint is 15 month RFS.

## 2.0 OBJECTIVES AND SCIENTIFIC AIMS

- The primary objective of the study is to determine if panitumumab with HAI in combination with systemic chemotherapy can increase the 15 month RFS for colorectal cancer patients with resected liver metastases.
- The secondary objectives are (1) to assess toxicity, (2) to determine survival, (3) to analyze tumor tissue for predictive biomarkers (such as NRAS, BRAF, PIK3CA, AKT1 and MEK1), and correlate with patient progression and survival following therapy. Most patients will have had RAS testing performed prior to protocol treatment; RAS will be analyzed at surgery if not performed previously. Frozen and paraffin-fixed tissue from the liver metastases will be available at surgery to measure these values.

### **3.0 BACKGROUND AND RATIONALE**

There are almost 150,000 new cases of colorectal cancer each year in the United States. Approximately 60% of patients develop hepatic metastases, and 15% are suitable for surgical resection. Of those who are able to undergo resection, 5-year survival is approximately 30% to 50%. About 200 patients each year undergo surgery at MSKCC for treatment of hepatic metastases, and approximately 100 undergo resection. Our older single institution experience with liver resection documents the efficacy of this aggressive approach with an actuarial two-year survival of 75%, but a two-year disease-free survival of only 21.2% in the subset of patients who underwent complete resection of colorectal liver metastases. Combined multi-institutional data from the registry of hepatic metastases was similar, with two-year actuarial survival and disease-free survivals of 65% and 35% respectively. These studies were conducted without standardized adjuvant chemotherapy post-surgical resection. Those least likely to be cured by resection of hepatic metastases are patients with node-positive primary, disease free interval  $\leq$  12 months,  $> 1$  tumor, tumor size  $\geq 5$  cm, CEA  $> 200$  ng/ml. Giving one point to each risk factor produces a Clinical Risk Score (CRS) between 0-5. Those with a risk score of 0 have a 60 percent five-year survival and those with a score of 5 have a 14 percent five-year survival. Therefore, we will use CRS to stratify patients.

Patients who do not undergo resection do not have favorable outcomes. Scheele et al reported no patient surviving 5 years if complete resection was not performed.

#### **3.1 Rationale for Treatment after Hepatic Resection**

##### **3.1.1 Recurrence-Free Survival**

RFS greatly depends on patient characteristics such as used in the Fong and Nordlinger scores, and can therefore vary from one study to another.

In data from our institution and in review of the surgical literature, patients who underwent complete resection of hepatic metastases from colorectal cancer were only afforded a 5-year actuarial overall survival of 33-50%, with a 5-year disease-free survival of only 22%. Therefore, approximately 75% of resected patients will recur, with 50% recurring in the liver and 50% recurring elsewhere. Of those patients who do recur, approximately 80% will do so in the first two years.

Our definition of recurrence will be any lesion growing in the liver or extrahepatic sites that is felt by the reference radiologist to be new disease. RFS or disease-free survival (DFS) as seen most recently in studies using systemic therapy or no therapy are listed below.

Publications	DFS/RFS at 15 months	Characteristics
---------------------	-----------------------------	------------------------

Kornprat (Annals of Surgical Oncology; Vol. 14, No. 3, 2007)	35%	All patients had greater than 4 metastases; largest median size 4.3 cm; 69% of patients were synchronous
Choti (Annals of Surgery; Vol. 235, No. 6, 2002)	40%	Patients with $\leq$ 3 and $>$ 3 metastases had a median DFS of 16 vs 8 months; Synchronous disease had a median DFS of 13 months
Nordlinger (Cancer; Vol. 77, No. 7, 1996)	40%	40% of patients were synchronous; 86% had 1-3 metastases; 12% had $>$ 4 metastases

### 3.1.2 Systemic Chemotherapy

Perioperative chemotherapy has shown to increase disease free survival. The EORTC randomized 364 patients with resectable liver metastases (1-4 metastases) to 6 cycles of FOLFOX4 pre-surgery and had 6 cycles post versus surgery alone. The endpoint was an improvement in disease free survival (DFS) which was not significant when all patients were included (7.3%, p=0.058). In eligible patients the DFS increased from 28% to 36% at 3 years with perioperative chemotherapy (p=0.041) which increased further to a 9.2% difference (p=0.025) when only resected patients were analyzed. Median followup time was 39 months.

Recurrence after liver resection is a significant problem with nearly 70% of patients developing recurrence, and the majority of recurrences occur in the first 2-years post resection. A Canadian and European Intergroup (EORTC-NCIC TG-GIVO) compared bolus FU/LV to surgery alone in 107 patients after liver resection and showed no increase in overall survival or DFS. The Fédération Francophone de Cancérologie Digestive (FFCD) trial randomized 173 patients after liver resection to bolus FU/FA or no further therapy. The end-point of the study was DFS which was 33.5% and 26.7% at 5 years in the treated and control arms, respectively. After adjusting for negative prognostic factors, there was a significant DFS advantage for the chemotherapy group (p=0.028). Sixty-nine percent of patients in this study had only one metastasis, and 72% had a  $>12$  month time interval from primary to metastases. With a median follow-up of 84.7 months, the median survival was 62 and 46 months for the treated and control patients, respectively (p=0.13).

A meta-analysis of these two studies with a total of 278 patients reported a median PFS of 27.9 and 18.8 months for chemotherapy versus control groups, respectively (p=0.058) and a median survival of 62.2 and 47.3 months, respectively (p=0.95). Patients in this study had very good risk factors; 69 % had only 1 metastasis, 66 % had Duke's B carcinoma and 67 % had liver recurrence documented one year after the primary. In their multivariate analysis, adjuvant chemotherapy was independently associated with improved PFS (p=0.026) and overall survival (p=0.046). The number of metastases ( $\geq 2$ ) was also associated with decreased PFS (p=0.022) and survival (p=0.023).

A European study randomized 151 patients to bolus/infusional 5FU/LV or FOLFIRI after liver resection. With a median follow-up of 42 months, the median DFS was 21.6 and 24.7 months for

the 5FU/LV and FOLFIRI groups, respectively ( $p=0.47$ ). On multivariate analysis, adverse factors associated with DFS included prior adjuvant chemotherapy for the primary tumor, diagnosis of liver metastases  $\leq 1$  year after the primary cancer, and  $>1$  liver lesion. There are currently no randomized trials to support adjuvant FOLFOX after liver resection. A Japanese trial of adjuvant FOLFOX started accrual in 2004 and enrolled only 60 patients, since 62 were excluded because of extrahepatic disease and 20 refused randomization, demonstrating some of the difficulty doing randomized trials in this setting. A newer study is accruing patients to hepatectomy followed by FOLFOX versus no further therapy.

Several retrospective series have shown a benefit for adjuvant treatment after liver resection. Parks and colleagues reported on 792 patients who had liver resections between 1991 and 1998. Multivariate analysis showed that positive margins ( $HR=1.59$ ), bilateral liver tumors ( $HR=1.39$ ) and adjuvant chemotherapy ( $HR=0.75$ ) were independent predictors of outcome. Patients who received adjuvant chemotherapy with a higher CRS had increased chances of surviving (1.3-2 times higher) compared with those patients who did not receive adjuvant treatment. Wang et al using the Seers-Medicare data base found 923 patients  $>65$  years of age who had liver metastases. The 5 year survival was 22%, which was increased with both systemic and HAI + SYS therapy after resection. A retrospective study from Korea compared of 156 patients who were treated after liver resection with FOLFOX, FOLFIRI or fluoropyrimidines alone. After median follow-up of 3.7 years, there was a non-significant difference among the three adjuvant regimens with respect to DFS ( $p=0.088$ ). [35% (FOLFOX), 25% (FOLFIRI) and 25% (fluoropyrimidines alone).] After adjusting for adverse prognostic variables there was a trend towards a greater benefit with FOLFOX ( $p=0.068$ ).

In summary, the administration of chemotherapy, with 5FU/LV after resection of liver metastases tends to improve prognosis and DFS. Irinotecan added to FU/LV did not improve results. Newer studies with post-op FOLFOX or XELOX with or without Cetuximab are ongoing by NSABP and European groups.

### 3.1.3 HAI Therapy after Hepatic Resection

Ackerman has demonstrated that microscopic metastases less than 1mm in size derive their blood supply from the portal circulation. As tumors begin to grow they induce the development of new vessels. Tumors measuring 1 to 2mm are encircled by new vessels derived from both the arterial and portal circulation, which mix freely. Tumors greater than 3mm have a well-developed arterial circulation. Metastases that remain after hepatic resection are probably in the range of 2 to 3mm and are therefore not detectable by the ultrasound scanning technique, which has a resolution of 5mm. Presumably, these metastases derive most of their blood supply from the arterial circulation. Therefore, adjuvant chemotherapy to the liver for resected hepatic metastases should be given via arterial circulation.

A number of studies randomized patients after liver resection to HAI plus systemic therapy versus no further therapy, or systemic chemotherapy alone. The Eastern Cooperative Oncology Group (ECOG) randomized 109 patients to HAI plus systemic versus no further therapy. The arms were well matched, and all patients had 1-3 resectable liver metastases. This study achieved its primary endpoint of an increase in DFS. The DFS at 4 years was 46% for the HAI group and 25% for surgery alone ( $p=0.04$ ).

A randomized study at MSKCC compared hepatic arterial infusion (HAI) and systemic therapy versus systemic chemotherapy alone. The study revealed a significant increase in hepatic disease-free survival in those patients who received HAI therapy in addition to systemic.

At 2 years, hepatic progression-free survival was 89% and 37% for the HAI + SYS vs. SYS alone groups. Median PFS was 31 and 17 months, respectively. Updated survival analysis reveals a median survival of 5.6 years for the HAI and 4.7 years for systemic alone. For patients with a poor clinical risk score of 3-5, the 10 year survival was 40% for the HAI + SYS group versus 18% for SYS group.

A study from Greece on 122 patients reported a significant improvement in 5 year DFS, 58% versus 34% (p=0.002), and 5 year survival, 73% versus 60% (p=0.05) for adjuvant HAI plus systemic chemo-immunotherapy versus systemic alone groups, respectively. A randomized study from Germany showed no improvement in DFS.

[figure not shown]
Modern chemotherapy such as irinotecan in combination with HAI FUDR/ Dexamethasone (Dex) in a phase I/II trial after resection of liver metastases yielded a 5 year survival of 59%. In a phase I trial with oxaliplatin + FU/LV added to HAI FUDR/Dex after liver resection, the 4 year overall survival was 88%. Alberts and colleagues reported results from the NSABP study of systemic capecitabine and oxaliplatin alternating with HAI FUDR after resection of liver metastases. The 2 year survival rate was 88% (95% CI 82-98%) with a median follow-up of 4.8 years. The 2 year overall recurrence was 59.7 %.

In a retrospective review, House et al evaluated patients who underwent liver resection between 2001-2005 and compared 125 patients who were treated with HAI plus modern systemic chemotherapy with those who received modern chemotherapy alone. They reported a 5 year survival of 72% and 52% (p=0.004) for the 2 groups, respectively. In a larger retrospective review at MSKCC of over 1,000 patients who underwent liver resection, a multivariate analysis demonstrated that one of the most significant factors leading to improved survival was postoperative HAI therapy. Those who received HAI therapy after hepatic resection had a median survival of 68 months versus 50 months for those who did not (p<0.001).

In our last four adjuvant studies, the patient population has been changing. Our surgeons are resecting patients with more disease. As we accrue patients with worse prognostic factors, the recurrence-free survival is decreasing. The table below reflects these characteristics.

Variables		HAI + 5FU/LV (n = 74) %	HAI + CPT-11 (n = 96) %	HAI + FOLFOX (n = 37) %	HAI + FOLFOX or FOLFIRI, +/- BEV (n = 73) %
# lesions (Pathology)	1	36	40	32	23
	2-4	45	47	57	43
	>4	19	13	11	33
Lesion Size	≥ 5cm	30	25	22	18
DFI	< 12 mos	77	74	62	79
Margins	≤ 1 mm	23	11	11	16

+ Margins	0 mm	15	4	5	10
Post-op CEA	> 5 ng/ml	26	33	16	21

Because of the increase in poor patient characteristics, the recurrence-free survival in our most recent study with HAI depicted above by the red line appeared to be inferior to previous adjuvant studies conducted at MSKCC with HAI (RFS was 59 % at 15 months). This is compared with a RFS of approximately 40 % at 15 months from recent studies evaluating systemic therapy (as reflected in the chart in section 2.1.1).

To fairly evaluate our next trial, we feel we should use as historical control a recurrence-free survival that reflects both what is in literature and our most recent trial. Therefore an RFS at 15 months of 50% (which is an average between the estimates in our study and in the other studies), will be considered as an appropriate historical control for the 15 months RFS.

This year at ASCO the N0147 trial (adjuvant cetuximab after stage III colon resection) was presented. Results will show no benefit for patients receiving cetuximab. Our proposed trial is for adjuvant therapy after liver resection. This patient population has a much higher rate of recurrence (especially outside the liver). Because of the good protection of the liver with HAI therapy, one of the common places for recurrence is lung and nodal disease. In my experience, both these areas benefit from anti-EGFR therapy. Therefore, we feel the addition of anti-EGFR agents to systemic therapy and HAI therapy may improve RFS after liver resection.

This trial will evaluate HAI therapy with systemic CPT-11+ 5FU/LV plus or minus panitumumab. Patients will be stratified by clinical risk score (1-3 vs 3 or greater) and previous chemotherapy (oxaliplatin vs irinotecan or no previous therapy).

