#### **14.0 BIOSTATISTICS**

This study will 1:1 randomize 78 patients to two treatment arms: HAI FUDR and dexamethasone with systemic chemotherapy, +/- systemic Panitumumab. Randomization procedures will be discussed in section 15.2.

The primary endpoint is 15 month recurrence free survival (RFS). Based on an exact binomial single stage design, with 39 patients in each arm we are able to differentiate between unacceptable 15 month RFS of 50% and acceptable 15 month RFS of 70% with type I error (falsely accepting a non-promising therapy) and II error (falsely rejecting a promising therapy) rates of 10 % each. For a particular arm, if 24 or more patients are alive and disease free at 15 months the regimen in that arm will be considered worthy of further investigation. We will use the —pick the winner— format based on the randomized phase II clinical trials approach proposed by Simon et al. (1985) to differentiate between 15 month RFS of 50% and 70%. The pick the winner role only occurs if both regimens are efficacious. If the number of patients who are disease free and alive at 15 months in one arm is at least 24 and it exceeds by at least 3 patients the number of alive and disease free patients at 15 months in the other arm, then the arm with the higher 15 months RFS would be declared the winner. If neither arm had at least 24 patients alive and disease free at 15 months, the regimens in both arms would be considered unworthy of further evaluation. The probability of selecting the better regimen is 85%; the probability that no regimen is selected is approximately 9%, while the probability of a tie is 6 % (Simon R, Wittes RE, Ellenberg SS. (1985). Randomized phase II clinical trials. *Cancer Treat Rep* 69, 1375-1381.)

RFS will also be estimated using the Kaplan Meier method. As secondary endpoint, overall survival will be estimated by the Kaplan Meier method. Associations between biomarkers and RFS and overall survival will be assessed using the log-rank test. In each arm, safety and tolerability will be summarized using descriptive statistics.

The prevalence of RAS mutations is about 40%; therefore we would have to approach about 120 patients in order to accrue 78 patients. On average, we see about 40 eligible patients per year; therefore we would need three years to reach 120.

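### The 50% floor averages HAI and non-HAI results although both arms receive HAI, so the stated 10% error is not the chance of accepting a panitumumab arm that adds nothing

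*Combined protocol and SAP*

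**What the plan says.** Sections 4.1 and 4.2 give HAI FUDR/dexamethasone and CPT-11/5FU/LV to all patients; the arms differ only by panitumumab. Sections 1.0 and 2.0 set the objective as whether 15-month RFS rises when panitumumab is added.

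Section 3.1.3 reports for HAI that "RFS was 59 % at 15 months" and contrasts this with roughly 40% elsewhere. Section 3.1.1 lists those other series (35%, 40%, 40%), introduced as "studies using systemic therapy or no therapy are listed below". The historical control combines the two sources: "Therefore an RFS at 15 months of 50% (which is an average between the estimates in our study and in the other studies").

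Section 14 carries this value into an exact binomial single-stage rule for each arm: "with 39 patients in each arm we are able to differentiate between unacceptable 15 month RFS of 50% and acceptable 15 month RFS of 70" per cent. Both error rates are set at 10%, and the pass mark is 24 of 39. A second step compares the arms: one is the winner if it has at least 24 successes and leads by at least 3. The stated selection probabilities are 85% for the better regimen, about 9% for no selection and 6% for a tie.

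**The concern.** A panitumumab arm that adds nothing performs like HAI plus chemotherapy. The protocol's only 15-month RFS estimate for an HAI regimen is 59%, which is 9 points above the rate called unacceptable. The floor is lower because it is averaged with series in a setting that neither arm is in. A regimen with no panitumumab effect could therefore clear the floor on the strength of its backbone, and a reader could take the pass as evidence for panitumumab. The winner step does compare the arms, but its properties are given only for 70% against 50%, a control rate below the protocol's own HAI figure. Section 14 plans no estimate of the between-arm difference that would answer the objective directly.

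**Working it through.** **Inputs.** n = 39 per arm, pass mark 24, rates 50% and 70%, lead of 3 (Section 14); HAI rate 59%, non-HAI about 40%, most recent HAI study n = 73 (Section 3.1.3). The 55% and 57% rates below are assumptions, added to show a range.

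**1. Origin of the floor.** (59 + 40)/2 = 49.5, taken as 50%.

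**2. The plan's own figures.** With X ~ Binomial(39, p), the pass probability is P(X ≥ 24).
- At p = 0.50: 0.0998. At p = 0.70: 0.9056. Both 10% error claims reproduce, and n = 39 is the smallest size that meets them.
- Winner rule, summed over all pairs (x, y) from two independent arms at 0.70 and 0.50: better arm 84.6%, none 8.5%, tie 6.2%. This matches 85/9/6.

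**3. Panitumumab adds nothing (both arms at the backbone rate).**

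| Backbone rate | Arm A reaches 24/39 | Arm A declared winner |
|---|---|---|
| 50% | 10.0% | 8.1% |
| 55% | 25.6% | 16.7% |
| 57% | 34.3% | 20.1% |
| 59% | 44.1% | 22.9% |

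At 59% the remaining outcomes are: Arm B winner 22.9%, tie 22.9%, neither arm passes 31.3%.

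**4. Panitumumab works (Arm A at 70%).**

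| Arm B rate | Arm A selected | Arm B selected | None | Tie |
|---|---|---|---|---|
| 50% | 84.6% | 0.7% | 8.5% | 6.2% |
| 59% | 65.2% | 5.1% | 5.3% | 24.4% |

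**5. Uncertainty in the 59%.** The event count is not given. Assuming 43/73 = 58.9%, the exact 95% interval is about 47% to 70%. Pass probabilities at those limits are about 5% and 91%.

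**6. Precision of the randomised difference.** The 95% half-width is 1.96 × √[(pA(1−pA) + pB(1−pB))/39]. With both arms at 0.59: 1.96 × √(0.4838/39) = 0.218. With both at 0.50: 0.222. With 0.70 against 0.59: 0.211. So it is about ±22 points.

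**The case against.** The strongest reply is that the floor is disclosed and reasoned. Section 3.1.3 describes worsening prognostic factors and falling RFS, and chooses a control that reflects both the literature and the latest trial. Section 14 defines type I error relative to 50%, and at that value its arithmetic is right. This stands: a reader might infer that the 10% is miscalculated, and it is not. The trend argument is weaker, because the text attributes the most recent HAI result to those worse characteristics, and no HAI estimate of 50% appears.

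The reply is also right that 24/39 is not the whole decision. A reader might take 44% as the chance that ineffective panitumumab is declared better. The lead of 3 brings that down to 23%. Nor is the chance that at least one arm passes when both are at 59%, 1 − (1 − 0.4406)² = 69%, a false-positive rate: if HAI plus chemotherapy truly gives 59%, calling Arm B worthy against a 50% floor is no error under the stated design.

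Finally, 59% cannot be treated as known. The table in Section 3.1.3 describes the latest study as FOLFOX or FOLFIRI with or without bevacizumab. This trial uses CPT-11/5FU/LV without bevacizumab, in all-RAS wild-type patients. The sentence giving 59% could also be read as referring to earlier HAI studies, although the averaging to 49.5 points to the latest one, and either way it is an HAI figure. If the latest rate is lower, 44% is too high. This justifies showing a range. It does not restore 10%, since the pass probability is still 26% at 55%.

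**Conclusion.** The point holds in a limited form. Section 14's figures are correct at 50% and 70%, but they do not describe a panitumumab arm that adds nothing to the treatment both arms receive. For backbone rates of 55% to 59%, such an arm passes the screen with probability 26% to 44% and is declared winner with probability 17% to 23%. At 59%, selection of a truly better 70% arm falls to 65%, mainly because ties rise to 24%.

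These results assume independent binomial outcomes, all 39 patients per arm evaluable at 15 months, and a backbone rate near the sponsor's HAI figure. They also read the winner rule as at least 24 successes plus a lead of at least 3, the reading that reproduces 85/9/6.

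A reader might go further and conclude that the floor must be 59%. The documents do not compel that. With n = 39, holding error to 10% at 59% needs a pass mark of 28 (7.0% error), which has only 48% power at the protocol's 70% target. It reaches 90% power only at 79%, a target found nowhere in the plan. Keeping 59% against 70% with both errors at 10% would need 126 patients per arm.

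**What to change.** In Section 14:

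1. Describe 24/39 as a minimum-activity screen against a blended historical rate, and say that passing it does not show a panitumumab effect.
2. Beside the 50%/70% figures, add the pass and winner probabilities at backbone rates of 55% to 59%, and the selection probabilities for 70% against 59%. Note that the 59% comes from a related regimen with n = 73.
3. Base the conclusion about adding panitumumab on the randomised Arm A minus Arm B difference in 15-month RFS with its 95% confidence interval, not on Arm A passing 24/39.

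Do not raise the pass mark to 28, for the power reason given above.

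Cost: protocol wording, less favourable stated error rates, and open acknowledgement that an interval of about ±22 points would only just exclude zero if the observed difference were the targeted 20 points or a little more. No extra patients are needed.
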